3.1 PATCH 2 and PATCH 3 Inclusion Criteria (See Study Process Flows)

- Willing and able to provide informed electronic consent via DocuSign
- Willing to report compliance with HCQ or Placebo (“tablets”) in the form of an on-line journal and participate in other forms of self-reporting (e.g., symptom tracker and experience log)

PATCH 2 & 3 TRIAL

- Willing and able to go to designated areas for testing (COVID-19/SARS-CoV-2 and/or serologic) and/or administer at home testing kits for study data collection purposes.
- Must be able to swallow and retain oral medication and must not have any clinically significant gastrointestinal abnormalities that may alter absorption such as malabsorption syndrome or major resection of the stomach or bowels
- Must have adequate baseline organ function
- Subjects meeting the following criteria by Sub-Study:

PATCH 2 Inclusion (Sub-Study 1): 50-75 years of age; self-reporting as having a fever within four days prior to time of enrollment; and not requiring hospitalization. Enrolled individuals will undergo testing for COVID-19 and sent home for self-quarantine. Patient must be willing and able to provide informed consent, agree to testing for COVID-19 at time of enrollment to confirm diagnosis, at the end of treatment (Day 15, 16 or 17) and two weeks after the end treatment (Day 29, 30 or 31) where Day 1 is defined as the first day blinded study drug is taken by the patient. (See Appendix- PATCH2 process flows)

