PATCH 3 Inclusion (Sub-Study 2): Currently employed as a health care worker ([name]; Doctor of Osteopathic Medicine, DO; Nurse Practitioner, NP; Physician's Assistant, PA; and [name] or other members of the medical care team with significant COVID-19 exposure); asymptomatic and presumed negative for COVID-19 (no confirmatory testing conducted); scheduled for an average of ≥ 20 hours per week of clinical care over the next two months (or equivalent indicating at least part-time employment). Participant will be asked to comply with their employer's potential or confirmed COVID-19 incident protocol and must agree to undergo COVID-19 testing per standard of care using an FDA approved method upon the presentation of symptoms indicative of an influenza like illness; if a confirmatory COVID-19 diagnosis is given, participant will be offered to cross-over to HCQ 600 mg qd for 14 days. At the end of the 60-day medication period, participants remaining undiagnosed for COVID-19 will undergo virus and serology testing. (See Appendix- PATCH3 process flows)

PATCH 2 & PATCH 3 Combined Exclusion Criteria

(See Study Exclusions and Content Job Aid)

- Allergy to hydroxychloroquine, 4 aminoquinolines, or quinine
- Known G6PD deficiency
- Pregnant or lactating or intention of becoming pregnant during the study as self-reported during enrollment screening
- Receiving any trial treatment drug for 2019-nCoV within 14 days prior to screening evaluation (off label, compassionate use or trial related)
- Known retinal disease including but not limited to macular degeneration, retinal vein occlusion, visual field defect, diabetic retinopathy
- History of interstitial lung disease severe emphysema or asthma, or chronic pneumonitis Current diagnosis of porphyria or psoriasis
- Serious intercurrent illness that requires active intravenous therapy, intense monitoring, or frequent dose adjustments for medication including but not limited to infectious disease, cancer, autoimmune disease, cardiovascular disease

PATCH 2 & 3 TRIAL

- Have undergone major abdominal, thoracic, spine or CNS surgery in the last two months, or plan to undergo surgery during study participation
- Is receiving cytochrome P450 enzyme-inducing anticonvulsant drugs (i.e. phenytoin, carbamazepine, Phenobarbital, primidone or oxcarbazepine) within four weeks of the start of the study treatment
- Currently taking digoxin
- History or evidence of increased cardiovascular risk including any of the following:

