9.5 Abnormal Laboratory Values

This trial does not require any safety laboratory assessments. However, in the event a participant has a standard of care lab completed which are self-reported and meet the DAIDS criteria for Grade 2 or greater, and cannot be attributed to another cause, study drug should be held and or reduced in accordance with section 8 above.

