Appendix 3: PATCH 2 Job Aid

PATCH2 STUDY LEAD JOB AID

A PATCH2 AUTOMATIC STUDY EXCLUSIONS	
Consumer Language for Enrollment Exclusions 
 These exclusions are automatic during the online enrollment experience in the enrollment portal If indicated exclusion response is selected, it is an automatic exclusion from the study 	Automatic Portal Exclusion
Are you between the ages of 50-75? [yes/ no]	If NO
Have you had a fever within the last four days? [yes/ no]	If NO
Do you require hospitalization? [yes/ no]	If YES
Are you able to self-quarantine at home for 14 days? [yes/ no]	If NO
Have you been tested for COVID-19? [yes/ no]	If NO

B AUTOMATIC CLINICAL EXCLUSIONS		
Consumer Language for Enrollment Exclusions 
 These exclusions are automatic during the online enrollment experience in the enrollment portal If “yes” to any, it is an automatic exclusion from the study. 	Automatic Portal Exclusion	
Protocol Language: Allergy to hydroxychloroquine, 4 aminoquinolines, or quinine	Do you have an allergy to hydroxychloroquine (HCQ), aminoquinolines, or quinine? [yes/ no]	X
Protocol Language: Patients with G6PD deficiency	Do you have a G6PD deficiency? [yes/ no]	X
Protocol Language: Pregnant or lactating or positive pregnancy test during pre-medication examination	Are you pregnant? [yes/ no]	X
	Are you breast feeding? [yes/ no]	X
Protocol Language: Receiving any trial treatment drug for 2019-ncov within 14 days prior to screening evaluation (off label, compassionate use or trial related)	Have you been in any other drug trial for COVID-19? [yes/ no]	X
Protocol Language: Patients with serious intercurrent illness that requires active infusional therapy, intense monitoring, or frequent dose adjustments for medication including but not limited to infectious disease, cancer, autoimmune disease, cardiovascular disease.	Are you on any IV or other serious medications, such as chemotherapy? [yes/ no]	X
Protocol Language: Patients who have undergone major abdominal, thoracic, spine or CNS surgery in the last 2 months, or plan to undergo surgery during study participation.	Have you had any surgery in the last two months? [yes/ no]	X
Protocol Language: Patients currently taking digoxin	Do you take the medication, digoxin or lanoxin? [yes/ no]	X
(From Medication Section)	Have you ever had a seizures? [yes/ no]	X
(From Medication Section)	Have you ever had a transplant? [yes/ no]	X

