Appendix 4: PATCH 3 Job Aid

PATCH3 STUDY LEAD JOB AID

A PATCH3 AUTOMATIC STUDY EXCLUSIONS	
Consumer Language for Enrollment Exclusions 
 These exclusions are automatic during the online enrollment experience in the enrollment portal If indicated exclusion response is selected, it is an automatic exclusion from the study 	Automatic Portal Exclusion
Are you a health care worker scheduled to working an average of 20 hours a week for the next 2 months?	If NO
Are you currently asymptomatic and presume not to have COVID?	If NO
Have you had a fever within the last four days? [yes/ no]	If NO
Do you require hospitalization? [yes/ no]	If YES
Are you able to self-quarantine at home for 14 days? [yes/ no]	If NO
Have you been tested for COVID-19? [yes/ no]	If NO

B AUTOMATIC CLINICAL EXCLUSIONS		
Consumer Language for Enrollment Exclusions 
 These exclusions are automatic during the online enrollment experience in the enrollment portal If “yes” to any, it is an automatic exclusion from the study. 	Automatic Portal Exclusion	
Protocol Language: Allergy to hydroxychloroquine, 4 aminoquinolines, or quinine	Do you have an allergy to hydroxychloroquine (HCQ), aminoquinolines, or quinine? [yes/ no]	X
Protocol Language: Patients with G6PD deficiency	Do you have a G6PD deficiency? [yes/ no]	X
Protocol Language: Pregnant or lactating or positive pregnancy test during pre-medication examination	Are you pregnant? [yes/ no]	X
	Are you breast feeding? [yes/ no]	X
Protocol Language: Receiving any trial treatment drug for 2019-ncov within 14 days prior to screening evaluation (off label, compassionate use or trial related)	Have you been in any other drug trial for COVID-19? [yes/ no]	X
Protocol Language: Patients with serious intercurrent illness that requires active infusional therapy, intense monitoring, or frequent dose adjustments for medication including but not limited to infectious disease, cancer, autoimmune disease, cardiovascular disease.	Are you on any IV or other serious medications, such as chemotherapy? [yes/ no]	X
Protocol Language: Patients who have undergone major abdominal, thoracic, spine or CNS surgery in the last 2 months, or plan to undergo surgery during study participation.	Have you had any surgery in the last two months? [yes/ no]	X
Protocol Language: Patients currently taking digoxin	Do you take the medication, digoxin or lanoxin? [yes/ no]	X

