(From Medication Section)	Have you ever had a seizures? [yes/ no]	X

PATCH 2 & 3 TRIAL

(From Medication Section)	Have you ever had a transplant? [yes/ no]	X
Protocol Language: History or evidence of increased cardiovascular risk including any of the following: 
 Left ventricular ejection fraction (LVEF) < institutional lower limit of normal. Baseline echocardiogram is not required; Current clinically significant uncontrolled arrhythmias. Exception: Subjects with controlled atrial fibrillation; History of acute coronary syndromes (including myocardial infarction and unstable angina), coronary angioplasty, or stenting within 6 months prior to enrollment; Current ≥ Class II congestive heart failure as defined by New York Heart Association. 	Do you have any heart disease such as congestive heart failure, history of heart attack, angina, arrhythmias or atrial fibrillation (also called AFib)? [yes/ no]	X

C STUDY LEAD DECIDED EXCLUSIONS

Consumer Language for Enrollment Exclusions

- These exclusions will be asked prior to the consent call through the study enrollment portal. “Yes” response do not trigger an automatic exclusion.
- “Yes” responses require a live conversation between the prospective participant and the study lead during live consent.
- If a medical consult is needed, then the study lead will conduct a medical consult with study PIs. Track all medical consult language in the study portal.
- Call the prospective study participant back with the final decision (yes or no) on enrollment. If he/she is eligible, then finish study consenting, and trigger tablet + journal shipment

DISEASE EXCLUSIONS

Protocol Language	Study Portal Language		
Eye Disease: Known retinal disease including but not limited to macular degeneration, retinal vein occlusion, visual field defect, diabetic retinopathy	Do you have eye disease? [yes/ no]		
	(if yes) Please describe. [open text]		
	INCLUDED IF:	MEDICAL CONSULTATION IF:	EXCLUSION IF:
	Wears eye glasses		Any eye disease

Protocol Language	Study Portal Language		
Lung Disease: History of interstitial lung disease, severe emphysema or asthma, or chronic pneumonitis unrelated COVID-19.	Do you have lung disease, such as asthma or emphysema? [yes/ no]		
	(if yes) Please describe. [open text]		
	INCLUSION IF:	MEDICAL CONSULTATION IF:	EXCLUSION IF:
	If moderate or controlled	If in question, then medical consult	If severe, then exclude

Protocol Language	Study Portal Language		

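### Two Section 3.1 exclusions, intended pregnancy and interstitial lung disease or chronic pneumonitis, do not match the job aids that Section 3.1 cites for applying them

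*Combined protocol and SAP*

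**What the plan says.** Section 3.1 contains two lists with different cross-references. The inclusion list points to the study process flows. The combined exclusion list points to the job aid on exclusions.

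On pregnancy, the exclusion list (repeated in the synopsis) reads "Pregnant or lactating or intention of becoming pregnant during the study as self-reported during enrollment screening". On lung disease it names a history of interstitial lung disease, severe emphysema or asthma, and chronic pneumonitis.

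Table B of each job aid has a pregnancy row. The text shown there as protocol language is "Pregnant or lactating or positive pregnancy test during pre-medication examination". The portal questions beside it are "Are you pregnant? [yes/ no"] and one on breast feeding.

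Table C of each job aid has a lung row. It reprints the criterion as "History of interstitial lung disease, severe emphysema or asthma, or chronic pneumonitis unrelated COVID-19". Its portal question asks about lung disease with asthma and emphysema as the examples. Its three decision columns include moderate or controlled disease, refer doubtful cases to medical consult, and exclude severe disease.

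**The concern.** An exclusion defined by self-report at screening works only if screening asks the question. If the portal and the study lead work from the job aids, intended pregnancy is not raised. A person with moderate or controlled interstitial lung disease also meets the job aid's column for inclusion while meeting the protocol's criterion for exclusion.

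What is at stake is participant safety and consistent application of eligibility. For pregnancy the exposure is mainly in PATCH 3, where no age limit is stated and study drug is taken daily for up to 60 days. PATCH 2 enrols people aged 50 to 75 and treats for 14 days. The protocol itself treats pregnancy as important: Section 10.4 requires the sponsor to be told of any pregnancy on therapy or within 120 days after the last dose.

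**Working it through.** No arithmetic applies. The check sets the Section 3.1 text beside the matching job-aid rows.

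| Item | Section 3.1 | Appendices 3 and 4 | Match? |
|---|---|---|---|
| Current pregnancy, lactation | Excluded | One question each, automatic exclusion | Yes |
| Intended pregnancy | Excluded, by self-report at screening | No question | No |
| Pregnancy test | Not mentioned | Printed as protocol language | No |
| Severe emphysema or asthma | Excluded | Excluded | Yes |
| Interstitial lung disease | Any history excluded | Included if moderate or controlled; excluded if severe | No |
| Chronic pneumonitis | Any history excluded | Same severity rule, plus a qualifier about COVID-19 | No |

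**Pregnancy.** The remaining questions in Tables A to C cover other topics: sub-study entry items, allergy, G6PD, other COVID-19 drug trials, intravenous or other serious medication, recent surgery, digoxin, seizures, transplant, heart, eye and lung disease, porphyria, psoriasis, and current medication. None reaches pregnancy intention. The written enrolment steps in Section 4.0 include neither a pregnancy test nor a pre-medication examination, so the wording labelled as protocol language corresponds to no procedure there.

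**Lung disease.** In Section 3.1 the word severe stands directly before emphysema or asthma. The job aid's own reprint has a comma after interstitial lung disease, which supports the same reading. The decision columns nevertheless apply one severity rule to the whole row. The mismatch is therefore within the row itself, and it is confined to interstitial lung disease and chronic pneumonitis.

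**Route into the trial.** Under Section 4.0 a person self-refers through an online checklist, the criteria are reviewed, consent is taken, and randomisation follows. The review step as written out names only age and fever (PATCH 2) or the health-care-worker items (PATCH 3). In Table C it is a yes answer that requires the live eligibility conversation. A question that is not asked cannot trigger it.

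**The case against.** **Other safeguards exist.** Section 4.0 has a criteria review before randomisation, registration records chronic medical problems, consent is a live call, and Section 3.1 lets the Co-PI and staff exclude for medical reasons. A yes on lung disease leads to a conversation, not to admission, and the study lead sees interstitial lung disease and chronic pneumonitis named on the same row. This stands as a reason why enrolment of excluded people is possible and not certain. It does not remove the mismatch. No readable text ties these steps to the two exclusions, and an intention to become pregnant is not a chronic medical problem.

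**The PATCH 3 job aid cannot be operating literally.** Its Table A excludes workers who are not asymptomatic and also those who have not had a recent fever, which would leave almost nobody to enrol. That is fair, and it is a reason not to infer actual enrolments from the printed tool. It does not supply the missing question.

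**A stronger reading is tempting for organ function and absorption.** Section 3.1 requires "Must have adequate baseline organ function" and says that participants "must not have any clinically significant gastrointestinal abnormalities that may alter absorption". Section 9.5 states: "This trial does not require any safety laboratory assessments". Neither job aid asks about these matters. The nearest item, "Have you had any surgery in the last two months? [yes/ no"], would miss an older bowel resection. A reader might infer that these criteria go unchecked. The documents do not support that. They are inclusion criteria, Section 3.1 refers them to the process flows, and the flow figures are not visible in the text reviewed. Absence from a list of exclusions does not show absence of a check.

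**Conclusion.** The point holds for two exclusions. Intended pregnancy has no question in either job aid, and the pregnancy row carries wording that is not in Section 3.1. The lung row is looser than Section 3.1 for interstitial lung disease and chronic pneumonitis. For asthma and emphysema the documents agree.

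The consequence is that people the protocol excludes could be enrolled. A reader might go further and conclude that they will be, or try to count them. The documents give no rate of intended pregnancy or of these lung conditions among those screened, so no number is offered.

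The conclusion assumes that the printed job aids reflect the questions in the portal, and that the process flows do not add the missing question or override the lung row. The sponsor can confirm both directly. No endpoint, alpha, power or sample-size figure changes. This is a safety and consistency correction that should be made. It does not undermine the analysis.

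**What to change.** 1. In Table B of the job aids, above all for PATCH 3, add a yes/no question on intention to become pregnant during the study. Replace the pregnancy-test wording with the current Section 3.1 text.
2. Reconcile the Table C lung row with Section 3.1 for interstitial lung disease and chronic pneumonitis, including the added COVID-19 qualifier. Which rule is right is for the sponsor to decide and is not judged here.
3. For organ function and swallowing or absorption, confirm that the process flows apply these inclusion criteria, since neither job aid does. Nothing more is asked on this item.

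The cost is one portal question and a job-aid revision, with screening very slightly longer.

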 - Left ventricular ejection fraction (LVEF) < institutional lower limit of normal. Baseline echocardiogram is not required
 - Current clinically significant uncontrolled arrhythmias. Exception: Subjects with controlled atrial fibrillation
 - History of acute coronary syndromes (including myocardial infarction and unstable angina), coronary angioplasty, or stenting within 6 months prior to enrollment
 - Current \geq Class II congestive heart failure as defined by New York Heart Association
- Deemed unable to participate for medical reasons identified by Co-PI and study staff

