4.0 PARTICIPANT REGISTRATION/PROCEDURES

The following information is to be provided at the time of registration to the trial:

Participant Identification Information for PATCH 2 & PATCH 3:

- Participant initials (first and last)
- Participant's chronic medical problems
- Gender
- Birth date (mm/yyyy)
- Race
- Ethnicity
- Nine-digit ZIP code
- State of residence
- County of residence
- Cell phone number and alternate numbers
- Email address

Participant Identification Information for PATCH 2 Only (Sub-study 1): Identify the number of fulltime inhabitants at the residence where the participant will stay during the 14-day self-quarantine as well as ages and sex of each co-inhabitant and relationship to the study participant.

Participant Procedure for PATCH 2 (Sub-Study 1) (See study process flows)

1. Interested participants self-refer for study by completing online eligibility checklist on study portal (www.patchstudy.com)
2. Review inclusion and exclusion criteria: participant is 50-75 years of age and self-reported as having a fever within the last four days will undergo swab testing for COVID-19 per clinical care guidelines and approach, and then sent home for a self-imposed quarantine
3. Reviews the study and the Informed Consent Form with the subject and obtains informed consent via DocuSign
4. Participant study ID is assigned, and subsequently, randomized into a study arm (HCQ or placebo).
5. Package containing blinded study drug, study journals (medicine log, symptom tracker and experience log) and study documents (details on aims, design, consent forms, and any additional instructions) delivered to address provided by participant as place of residence during period of self-quarantine. Day 1 is defined as the first day the blinded study drug is taken by the participant
6. Lab provides participant's COVID-19 test results to designated Co-PI with designee
7. PI or designee calls participant informing them of result, discussing how to proceed on the trial (if positive, continue taking medication; otherwise, stop) and documenting discussion.
8. Each day, participants will record 1) temperature (to be reported twice daily, either via thermometer or self-report); 2) time medication taken; 3) any symptoms and AEs; and 4) if any co-inhabitants develop symptoms and/or become positive for COVID-19 (confirmed by accepted testing methods)

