9. Three times a week, participants will be called by clinical research coordinators to assess AEs and symptoms with all discussions well-documented. Clinical research coordinators may clinically escalate any medical determinations to Co-PI
10. After Day 14, which marks the end of the treatment period, participants will no longer be expected to continue self-reporting information into the study portal. Participant will undergo follow-up testing for COVID-19 at two additional time points. The first will be either day 15, 16 or 17, with the second on either on day 29, 30 or 31
11. If during active participation, the participant reports worsening of symptoms related to COVID-19 from baseline, this is reported to the PI for further clinical evaluation

Participant Procedure PATCH 3 (Sub-Study 2) (See study process flows)

1. Interested participants self-refer for study by completing online eligibility checklist on study portal (www.patchstudy.com)
2. Review inclusion and exclusion criteria:
 - Currently employed as a health care worker ([name]; Doctor of Osteopathic Medicine, DO; Nurse Practitioner, NP; Physician's Assistant, PA; and [name] or other members of the medical care team with significant COVID-19 exposure);
 - Asymptomatic and presumed negative for COVID-19 (no confirmatory testing conducted);
 - Scheduled for an average of >20 hours per week of clinical care over the next two months (or equivalent indicating at least part-time employment).
 - Willing to comply with their employer's potential or confirmed COVID-19 incident protocol
 - Agrees to undergo COVID-19 testing per standard of care using an FDA approved method upon the presentation of symptoms indicative of an influenza like illness (if a confirmatory COVID-19 diagnosis is given, participant will be offered to cross-over to HCQ 600 mg qd for 14 days.)
3. Reviews the study and the Informed Consent Form with the subject and obtains informed consent via DocuSign
4. Participant study ID is assigned, and subsequently, randomized into a study arm (HCQ or placebo).

PATCH 2 & 3 TRIAL

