PATCH 2 & 3 TRIAL

Protocol Language: History or evidence of increased cardiovascular risk including any of the following:
 
 • Left ventricular ejection fraction (LVEF) < institutional lower limit of normal. Baseline echocardiogram is not required; • Current clinically significant uncontrolled arrhythmias. Exception: Subjects with controlled atrial fibrillation; • History of acute coronary syndromes (including myocardial infarction and unstable angina), coronary angioplasty, or stenting within 6 months prior to enrollment; • Current ≥ Class II congestive heart failure as defined by New York Heart Association. 	
Do you have any heart disease such as congestive heart failure, history of heart attack, angina, arrhythmias or atrial fibrillation (also called AFib)? [yes/ no]
	
X

---	---	-----------------

C STUDY LEAD DECIDED EXCLUSIONS

Consumer Language for Enrollment Exclusions
 
 • These exclusions will be asked prior to the consent call through the study enrollment portal. “Yes” response do not trigger an automatic exclusion. • “Yes” responses require a live conversation between the prospective participant and the study lead during live consent. • If a medical consult is needed, then the study lead will conduct a medical consult with study PIs. Track all medical consult language in the study portal. • Call the prospective study participant back with the final decision (yes or no) on enrollment. If he/she is eligible, then finish study consenting, and trigger tablet + journal shipment

DISEASE EXCLUSIONS

Protocol Language	Study Portal Language		

Eye Disease: Known retinal disease including but not limited to macular degeneration, retinal vein occlusion, visual field defect, diabetic retinopathy
	
Do you have eye disease? [yes/ no]
		
	
(if yes) Please describe. [open text]
		
	
INCLUDED IF:
	
MEDICAL CONSULTATION IF:
	
EXCLUSION IF:

	
Wears eye glasses
		
Any eye disease

Protocol Language	Study Portal Language		

Lung Disease: History of interstitial lung disease, severe emphysema or asthma, or chronic pneumonitis unrelated COVID-19.
	
Do you have lung disease, such as asthma or emphysema? [yes/ no]
		
	
(if yes) Please describe. [open text]
		
	
INCLUSION IF:
	
MEDICAL CONSULTATION IF:
	
EXCLUSION IF:

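### Porphyria and psoriasis: the synopsis and Section 3.1 exclude any current diagnosis, but the job aids in Appendices 3 and 4 admit moderate or controlled disease

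*Combined protocol and SAP*

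**What the plan says.** The combined exclusion list in Section 3.1, which covers PATCH 2 and PATCH 3, excludes a "Current diagnosis of porphyria or psoriasis". The synopsis uses the same words. Neither place qualifies them by severity, control or specialist care. The list opens with a pointer, "See Study Exclusions and Content Job Aid", but does not say what happens if the job aid differs.

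The job aids are Appendix 3 (PATCH 2) and Appendix 4 (PATCH 3). Both place porphyria and psoriasis in part C, among the exclusions that the study lead decides. A yes answer there does not exclude automatically. Such answers "require a live conversation between the prospective participant and the study lead during live consent". The outcome can be enrolment: "If he/she is eligible, then finish study consenting, and trigger tablet + journal shipment".

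The porphyria and psoriasis row has two components in each appendix:

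- The protocol-language cell makes these patients ineligible, because the disease may worsen, unless it is well controlled and a treating specialist has agreed to watch for flares.
- The decision cells include moderate or controlled disease, refer doubtful cases for a medical consult and exclude severe disease.

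**The concern.** One criterion is stated in ways that cannot all be followed. The body of the protocol gives an absolute exclusion. The protocol-language cell gives a conditional one and presents it as the protocol's wording, which it is not. The decision cells give a severity test.

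The study lead works from the job aid, so the most permissive version is the one most likely to operate at screening. At stake is whether people whom the protocol body excludes for safety are enrolled and sent drug: 800 mg daily for 14 days in PATCH 2, or 600 mg daily for up to 60 days in PATCH 3. Screening carries much of the protection in this trial. It is run virtually, requires no safety laboratory tests (Section 9.5), and in PATCH 3 relies on self-report alone for adverse events (Section 8.4).

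**Working it through.** No arithmetic applies. The check is to set the texts side by side and then ask how each would treat the same applicant.

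**The rules as written**

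| Source | Who is excluded | Who may enter |
|---|---|---|
| Synopsis; Section 3.1 | Anyone with a current diagnosis | Nobody with a current diagnosis |
| Appendices 3 and 4, protocol-language cell | Disease not well controlled, or no specialist agreeing to monitor | Well-controlled disease with a monitoring specialist |
| Appendices 3 and 4, decision cells | Severe disease | Moderate or controlled disease; doubtful cases go to a consult |

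**The same applicants under each rule** (decision cells read on their own)

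| Applicant | Section 3.1 | Protocol-language cell | Decision cells |
|---|---|---|---|
| Well controlled, specialist monitoring | Exclude | Eligible | Include |
| Well controlled, no specialist | Exclude | Ineligible | Include |
| Moderate, not well controlled | Exclude | Ineligible | Include |
| Severe, not well controlled | Exclude | Ineligible | Exclude |

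The three texts agree only on the last applicant. For the second and third, the decision cells contradict both Section 3.1 and the cell beside them.

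**A likely origin (inference).** The decision cells for this row match those of the lung-disease row word for word. A severity test suits that row, because Section 3.1 itself grades the lung criterion: "History of interstitial lung disease severe emphysema or asthma, or chronic pneumonitis". It attaches no grade to porphyria or psoriasis.

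**Whether another step would catch the error**

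1. The live call is mandatory after a yes answer, but this row guides its outcome.
2. The medical consult is triggered only when the study lead is in doubt. Clearly moderate or controlled disease need not reach it.
3. Section 4.0, step 2, comes before consent and randomisation in both sub-studies. For PATCH 2 it reads "Review inclusion and exclusion criteria: participant is 50-75 years of age and self-reported as having a fever within the last four days". The PATCH 3 step also starts "Review inclusion and exclusion criteria" and then lists only inclusion items. Neither says whether to review against Section 3.1 or the job aid.
4. The catch-all, "Deemed unable to participate for medical reasons identified by Co-PI and study staff", lets staff exclude further people by judgement. It does not settle which listed rule applies.

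**The case against.** The strongest defence has four parts.

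**Precedence may be stated elsewhere.** Some pages and the enrolment process-flow figures were not available to this review, and a precedence statement could sit there. That is a fair limit, so the claim that nothing settles precedence covers the available text only. A precedence sentence would still leave the job aid at odds with itself, because moderate disease without a specialist is not well-controlled disease with one.

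**The decision cells may be shorthand.** They sit beside the fuller condition, so a study lead could read the specialist requirement into them. That reading is possible, and the cells merely fail to repeat the requirement. But moderate does not mean well controlled, and even the fuller condition admits people whom Section 3.1 excludes.

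**Other safeguards narrow the exposed group.** Section 7.2 and both job aids bar methotrexate, azathioprine, TNF-alpha blockers and corticosteroids above 10 mg/day of prednisone or equivalent. Section 3.1 also excludes serious intercurrent illness that needs intense monitoring, registration records chronic conditions, and Section 8.5 reduces or holds the dose for adverse events. PATCH 2 participants are telephoned three times a week. These points stand, and they would catch some people with psoriasis. The drug bans do not address porphyria or psoriasis treated topically, and the on-treatment rules act only after exposure.

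**The matter is small.** It concerns one row in each of two appendices and does not touch the primary analysis. That is right and limits the weight of the point. It does not remove the contradiction.

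**Conclusion.** The inconsistency is real and needs correcting. The synopsis and Section 3.1 exclude every current diagnosis of either condition. The decision cells in both job aids admit moderate or controlled disease, and they also fall short of the condition in their own row. The conflict applies to both sub-studies.

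Its size in participants is unknown, because the documents give no prevalence for either condition. No count is offered. This is a point about consistent eligibility and participant safety. Sample size, power and alpha do not depend on it. The conclusion rests on the text available to this review and on reading the decision cells as the working instruction to the study lead, which is how part C is laid out.

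**What to change.** **Preferred.** In Appendices 3 and 4, change the protocol-language cell of this row to "Current diagnosis of porphyria or psoriasis" and set the decision to exclude on a yes to either question. Delete the inclusion and consult cells from this row only; they fit the lung-disease row and should stay there.

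**Alternative.** If the sponsor's clinicians want the exception, state the full condition (well controlled, and under a specialist who agrees to monitor for exacerbations) identically in Section 3.1, the synopsis and both decision rows.

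A sentence saying that Section 3.1 prevails over the job aids would be a useful addition. It does not replace either edit, because the row would still contradict itself.

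**Cost.** The preferred fix edits one row in each of two appendices. It loses an unknown number of applicants with moderate or controlled disease, all of whom Section 3.1 already excludes. The alternative also changes the eligibility criterion in Section 3.1 and the synopsis. Neither changes sample size, power or alpha.
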